9.2.	Sample Size and Power Calculations	69
9.3.	Analysis Populations	69
9.4.	Demographics and Baseline Characteristics	69
9.5.	Efficacy Endpoints	69
9.6.	Statistical Methods	70
9.6.1.	Efficacy Analysis	70
9.6.2.	Subgroup Analyses.....	70
9.6.3.	Pharmacokinetic Analysis	70
9.6.4.	Interim Analysis	70
9.7.	Safety Analysis.....	70
9.7.1.	Adverse Events.....	70

9.7.2.	Physical Examinations	71
9.7.3.	Concomitant Medication	71
9.7.4.	Vital Signs	71
		
9.7.6.	Clinical Laboratory Values	71
9.7.7.	Safety ECG (12-lead ECG)	71
10.	REGULATORY REQUIREMENTS	72
10.1.	Pre-Study Documentation	72
10.2.	Investigator Obligations	72
10.3.	Patient Confidentiality	72
10.4.	Informed Consent	72
10.5.	Independent Ethics Committee (IEC) Human Research Ethics Committee (HREC)	73
11.	PROTOCOL MANAGEMENT AND ADMINISTRATIVE CONSIDERATIONS	74
11.1.	Study Documentation	74
11.2.	Protocol Interpretation and Compliance	74
11.3.	Study Monitoring	74
12.	PRINCIPAL INVESTIGATOR SIGNATURE PAGE	75
13.	REFERENCES	77
SPONSOR PROTOCOL SIGNATURE PAGE		80
Appendix 1	Summary of Changes by Amendment	81

LIST OF IN-TEXT TABLES

LIST OF IN-TEXT FIGURES

Figure 1.	Schematic of APD334-010 Study Design	33
-----------	--	----

[figure not shown]
SYNOPSIS

[figure not shown]
Protocol Number:	APD334-010
Name of Drug:	Etrasimod (APD334)
Title:	An Open-label, Pilot, Proof of Concept Study to Evaluate the Safety, Tolerability, and Efficacy of Oral Etrasimod (APD334) in Patients with Primary Biliary Cholangitis
Indication:	Primary Biliary Cholangitis (PBC)
Study Phase:	Phase 2
Sponsor:	Arena Pharmaceuticals, Inc. [name], United States
Name of Sponsor Contact:	[REDACTED], MD, MHS [REDACTED] Research and Development & CMO Arena Pharmaceuticals, Inc. [name], US Tel: [REDACTED] Email: [REDACTED]
Name of Principal Investigator(s):	Multicenter
Medical Monitor:	[REDACTED], MD Medical and Safety [REDACTED] Arena Pharmaceuticals, Inc. [name] Switzerland Tel: [REDACTED] Email: [REDACTED]
Test Product, Dose and Mode of Administration:	Etrasimod 1 mg tablet per os (p.o.) with possible dose escalation to 2 mg p.o., based on available pharmacokinetic (PK) and safety data (vital signs and electrocardiogram [ECG]). [REDACTED]

	
Background	
Etrasimod is an orally available, selective, sphingosine 1-phosphate 1 (S1P₁) receptor modulator. S1P is a signaling sphingolipid required by lymphocytes to exit the lymphoid tissue and enter the bloodstream via a chemotactic gradient. The S1P₁ receptor is a physiological mediator that has been shown to regulate lymphocyte recirculation between lymphoid tissue and blood. Binding and internalization of the S1P₁ receptor may result in lymphocyte retention within lymphoid tissue, with subsequent reduction in peripheral lymphocyte count and lymphocyte availability for recruitment to sites of inflammation. S1P₁ receptor surface expression is required for S1P gradient-mediated lymphocyte migration out of lymphoid tissue into the circulation¹.
 
Modulators of the S1P₁ receptor, such as etrasimod, block lymphocyte migration out of the lymph tissue through internalization of the receptor, resulting in a sequestration of lymphocytes¹. Recent clinical development of S1P₁ receptor modulators has demonstrated their effect on resulting lymphocyte sequestration, and their potential for treating multiple autoimmune and chronic inflammatory diseases.
 
Rationale for use of etrasimod in treatment of PBC
 
Histologically, PBC is characterized by florid bile duct lesions with damage to biliary epithelial cells, dense portal inflammatory infiltrate and progressive loss of small intrahepatic bile ducts. T cells are important players in the pathogenesis of PBC. The disease results from a chronic inflammatory process in which T cells attack the small bile duct epithelial cells. These epithelial cells eventually disappear, causing cholestasis and further progression of PBC. The T cells seem to be of both CD4⁺ and CD8⁺ origin, as shown by immunohistochemical staining in portal and periportal areas². The trigger of this autoimmune disease is unknown, but genome-wide association studies have suggested the importance of certain HLA variants and other immune-related genes, such as components of the IL-12 signaling cascade. Furthermore, more than 95% of patients also develop a humoral autoimmune response to mitochondrial proteins (i.e., antimitochondrial antibodies, AMA)^{2,3}.
 
The reduced peripheral lymphocyte availability seen with the S1P₁ modulator etrasimod is expected to decrease both CD4⁺ and CD8⁺ T cell recruitment to sites of inflammation, such as around the bile ducts. In addition to S1P₁ modulation, the

[figure not shown]
	
The screening period will last 5 to 8 weeks and will be followed by a 24-week treatment period, which includes assessment of safety, PK, tolerability and efficacy in up to 20 patients. During the treatment period, patients will need to take 1 tablet of study medication once per day (q.d.). The last dose is planned to be taken one day before the end of the treatment period (during Week 24). A follow-up visit will take place 2 weeks after the end of treatment. Please refer to the Schedule of Procedures and Visits (Table 1) for the detailed plan.
 
Screening Period (5 to 8 weeks before baseline visit):
 
Each patient will be asked to visit the study site at least 2 times for screening assessments within the 8 weeks prior to the planned start of the treatment (Day 1). Screening Visit 1 is to occur between Week -8 and Week -5. Screening Visit 2 is to occur at least 4 weeks from Screening Visit 1. For patients with ALP, ALT, AST, or total bilirubin values from Screening Visits 1 and 2 that are not within 20% of each other (see Inclusion Criterion 9), an unscheduled visit within the screening period may be conducted to repeat these assessments.
 
All patients must be consented before any study specific procedure is performed and written informed consent must be obtained. Patients will then undergo screening procedures to determine eligibility.
 
[REDACTED]
 
Treatment period (24 weeks):
 
Patients will come to the clinic [REDACTED]. Vital signs and ECG changes will be monitored extensively during this time, and PK sampling will be performed (6.13). Patients will receive a 1 mg etrasimod tablet (p.o., q.d.) from Day 1 onwards. If the 1 mg dose is well tolerated and there are no clinically significant changes in vital signs and ECG, the 1 mg dose level will be maintained. If 1 mg is not tolerated, then treatment will be stopped per the dose-stopping rules (see below). The 1 mg dose level may be increased to 2 mg at Week 12, based on the patient's safety and PK data. This data will be reviewed by a safety and dose escalation committee who will decide whether or not to proceed with 2 mg treatment. Patients with dose escalation on Week 12 will have PK sampling [REDACTED] (6.13), and vital signs and ECG monitoring performed [REDACTED].
 
Visits [REDACTED]: Patients will return to the study site and all planned examinations as described in Schedule of Procedures and Visits (Table 1) will be conducted. [REDACTED] only dose escalated patients will visit. Last dose of

--	--

[figure not shown]
[figure not shown]
[figure not shown]
	
study medication is planned 1 day before the end of the treatment visit at Week 24.
 
Follow-up Visit/End of Study Visit:
 
Visit Week 26, 2 weeks after end of treatment: Patients will return to the study site for the final visit, and final procedures will be performed per Schedule of Procedures and Visits (Table 1).
 
Premature Discontinuation: All procedures planned for Weeks 24 and 26 visits should be performed for all patients who discontinue the study prematurely.

Dose-stopping Rules:
	
Any of the following findings in a patient during treatment will lead to a stop in etrasimod dosing in the affected patient:
 
 1. Certain ECG changes (see details in text below), or 2. Clinical evidence of drug-induced liver injury (DILI; as described in 6.15) 
As described in the study plan above, at the discretion of the PI, the dose of etrasimod may be adjusted from 2 mg q.d. back to 1 mg q.d. if deemed necessary. If the patient is on 1 mg, the PI may discontinue etrasimod treatment if deemed necessary based on the dose-stopping rules.
 
Close Observation for Possible DILI:
 
It is critical to initiate close observation immediately upon detection and confirmation of early signals of possible DILI, and not to wait until the next scheduled visit or monitoring interval. Close observation is mandatory for any study subject who meets one or more of the following “possible DILI” laboratory criteria:
 
 • ALT or AST that is <ULN at baseline, followed by ALT or AST increase to >3 × ULN • ALT or AST that is >ULN at baseline, followed by ALT or AST increase to >2 × baseline • ALP >2 × baseline • Total bilirubin >1.5 × ULN 
Close observation includes:
 
 • Repeating liver enzyme and serum bilirubin tests within 48-72 hours. Then, repeating liver enzyme and serum bilirubin tests two or three times weekly. Frequency of retesting can decrease to once a week or less if abnormalities resolve, abnormalities stabilize, or the study drug has been discontinued and the subject is asymptomatic. • Obtaining a more detailed history of symptoms and prior or concurrent diseases.

[figure not shown]
[figure not shown]
	
• Obtaining a history of concomitant drug use (including nonprescription medications and herbal and dietary supplement preparations), alcohol use, recreational drug use, and special diets.• Ruling out acute viral hepatitis types A, B, C, D, and E; autoimmune or alcoholic hepatitis; nonalcoholic steatohepatitis; hypoxic/ischemic hepatopathy; and biliary tract disease.• Obtaining a history of exposure to environmental chemical agents.• Obtaining additional tests to evaluate liver function, as appropriate (e.g., INR, direct bilirubin).• Considering consultations, imaging studies, and/or therapeutic interventions, as required. 
Study Drug Discontinuation for Suspected DILI:
 
Should any patient who meets “possible DILI” laboratory criteria have persistence or worsening of lab data (i.e., ALT, AST, ALP, and/or total bilirubin) after one week of close observation, study drug must be discontinued. In addition, immediate study drug discontinuation is mandatory for any study patient who meets one or more of the following “suspected DILI” clinical criteria:
 
• ALT or AST $<2 \times$ ULN at baseline, followed by ALT or AST increase to $>5 \times$ baseline• ALT or AST $\geq 2 \times$ ULN but $<5 \times$ ULN at baseline, followed by ALT or AST increase to $>3 \times$ baseline• ALT or AST increase to $>2 \times$ baseline AND concomitant total bilirubin increase to $>2 \times$ baseline• ALT or AST increase to $>2 \times$ baseline AND concomitant INR increase >0.2• Clinical signs and symptoms of liver inflammation, including but not limited to fatigue, nausea, vomiting, right upper quadrant pain or tenderness, fever, rash, jaundice, icterus, and/or eosinophilia ($>5\%$) 
ECG changes:
 
Safety ECGs will be recorded on an ECG machine (12-lead), they will be printed and reviewed on-site by the PI or another physician (e.g., cardiologist). Typically, all safety ECGs will be obtained as single tracings, except for the pretreatment ECG obtained on Day 1, which is a triplicate recording.
 
--	--

	
Study Site(s):	Multicenter.
Study Population:	Patients with confirmed PBC diagnosis who fulfill the eligibility criteria.
Inclusion Criteria:	
Inclusion and exclusion criteria that refer to an assessment being performed “at screening” are referring to Screening Visit 1 unless specified otherwise.
 
1. Males or females aged 18 to 80 years (inclusive) at the time of screening, with confirmed PBC diagnosis based upon at least 2 of 3 criteria:
• AMA titer >1:40 on immunofluorescence or M2 positive by enzyme-linked immunosorbent assay (ELISA) or positive PBC-specific antinuclear antibodies (anti-GP210 and/or anti-SP100)• ALP >1.5 × ULN for at least 6 months• Liver biopsy findings consistent with PBC

	
2. Use of UDCA for at least 6 months prior to screening (stable dose for at least 3 months immediately prior to screening)
 
[REDACTED]
 
4. Patients must have the following laboratory parameters at screening
 
• ALP $>1.5 \times \text{ULN}$ but $<10 \times \text{ULN}$ (at all screening visits)• ALT and AST $<5 \times \text{ULN}$ (at all screening visits)• Total bilirubin $<\text{ULN}$ (at all screening visits) 
[REDACTED]

--	---

	 
8. AST, ALT, ALP, and total bilirubin must have 2 values at least 4 weeks apart that are within 20% of each other.

Exclusion Criteria	
1. Chronic liver disease of a non-PBC etiology. However, PBC patients accompanied with primary Sjögren’s syndrome (pSS) are eligible to be enrolled.
 
2. History or evidence of clinically significant hepatic decompensation:
  
3. Medical conditions that may cause non-hepatic increases in ALP (e.g., Paget’s disease)
  
7. Infection with hepatitis C virus anytime in the past; confirmed active infection with hepatitis B virus at screening.

	 
13. Treatment with obeticholic acid (OCA) or fibrates (including bezafibrate) within 30 days prior to Day 1.
 
14. Other immunosuppressive, immunomodulating or antineoplastic agents not listed in Permitted Medications section (6.17.1) within 30 days prior to Day 1 (or not meeting the stability time period for concomitant medications indicated as permitted).
 
--	---

Duration of the Study (per Patient):	Up to 34 weeks total : with 5 to 8 weeks for screening, followed by a 24-week treatment period (including a 12-week 1 mg treatment period followed by a 12-week 2 mg treatment period if

	tolerable) and a follow-up visit 2 weeks after the end of treatment.
Sample Size:	Up to 20 patients total
Efficacy Endpoints:	
 • Change from baseline to Week 12 and 24 in serum ALP concentration. • Change from baseline to Week 12 and 24 in: 
 ○ Complete blood counts (including lymphocytes and subset thereof). ○ hsCRP, ALT, AST, GGT, [REDACTED] C4 and [REDACTED] serum concentrations. ○ Total serum IgG, IgM, and AMA. ○ QoL, pruritus and fatigue (using PBC-40 and 5-D pruritus scales). ○ Ophthalmological examinations: 
 ▪ The Schirmer Test ▪ [REDACTED] Test in patients with abnormal results at screening
Safety Assessments:	
The following will be captured to assess the safety endpoints:
 
 - Clinical laboratory tests, including hematology, serum chemistry, coagulation, and urinalysis - [REDACTED] - Vital sign measurements - [REDACTED] - Safety 12-lead ECG - Physical and neurological examination - Adverse event reporting
Pharmacokinetic Assessments	
Patients will have a serial PK sampling [REDACTED]
 
[REDACTED]
 
[REDACTED] All PK samples are to be collected [REDACTED] of the scheduled timepoint.

	
PK data [REDACTED] will support the dose escalation of etrasimod in PBC patients at Week 12. An additional PK blood sample will be collected, if possible, at the time of any intolerable AE or SAE.
 
Samples will be analyzed for etrasimod and its putative metabolites (if possible). After the completion of study, samples will be transferred to sponsor designated storage site in US, and retained for future exploratory research related to the study drug. In general, the storage time is no more than 3 years.

Statistical Analyses:	
There is no formal sample size estimation for this proof-of-concept open label study. A sample size of up to 20 patients is reasonable to assess the efficacy and safety of etrasimod in the target population. An interim analysis of safety and efficacy may be performed when up to half of patients have finished 12 weeks of treatment.
 
Pharmacokinetic parameters will be calculated using non-compartmental methods. [REDACTED]
 
Summary statistics and appropriate graphic displays will be provided for PK and PD parameters, biomarkers and efficacy (ALP changes). Safety information after administration of etrasimod will be evaluated by tabulating adverse events and clinical assessment of clinical laboratory data by treatment period and follow up period.
 
Confidence interval of key efficacy measures will be also produced for non-inferential comparisons with published data.
 
Exploratory analysis of main study endpoints may be performed in subset of patients of medical interests, such as patient demographics, baseline ALP levels, baseline disease characteristics, biomarker, previous disease treatment received, etc. [REDACTED]

Date	27 June 2018

IEC	Independent Ethics Committee
IND	Investigational New Drug
IRB	Institutional Review Board
INR	international normalized ratio
█	█
█	█
kg	Kilogram
LDH	lactate dehydrogenase
L	Liter
MCH	mean corpuscular hemoglobin
MCV	mean corpuscular volume
MedDRA	Medical Dictionary for Regulatory Activities
mg	Milligram
█	█
NK	natural killer
NOAEL	no observed adverse effect level
█	█
OTC	over-the-counter
PBC	peripheral biliary cholangitis
PBL	peripheral blood lymphocyte
PD	Pharmacodynamics
PFT	pulmonary function test
PGA	Physicians Global Assessments
PI	Principal Investigator
PK	Pharmacokinetics
p.o.	per os (orally)
█	█
pSS	primary Sjögren's syndrome
PVG	Pharmacovigilance
q.d.	quaque die (once daily)
SAP	statistical analysis plan
S1P	sphingosine 1-phosphate
SAE	serious adverse event
SBP	systolic blood pressure
SD	standard deviation
sec	Second
SOP(s)	standard operating procedure(s)
t _{1/2}	elimination half-life
t _{max}	the median time to reach maximum plasma concentration

[REDACTED]

[REDACTED]

[REDACTED]

[REDACTED]

UDCA

ursodeoxycholic acid

ULN

upper limit of normal

VS

vital signs

[REDACTED]

[REDACTED]

WBC

white blood cell

WHO

World Health Organization

WHODRUG

World Health Organization Drug Dictionary

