3. INVESTIGATIONAL PLAN

3.1. Overall Study Design and Plan

This is an open label, single arm, multi-center clinical study to assess the safety and tolerability, PK and efficacy of etrasimod in patients with PBC. The trial will include adult patients, 18-80 years of age, with a confirmed PBC diagnosis, and who had an inadequate response to UDCA.

The screening period will last 5 to 8 weeks and will be followed by a 24-week treatment period. All patients will receive 1 mg etrasimod for 12 weeks followed by a potential dose increase to 2 mg etrasimod for 12 weeks. Those patients who do not dose escalate will remain on 1 mg etrasimod for the duration of the study through Week 24 (Figure 1). During the treatment period, patients will need to take 1 tablet of study medication (p.o. q.d.). The last dose is planned to be taken one day before the end of the treatment period (during Week 24). A follow-up visit will take place 2 weeks after the end of treatment. Please refer to the Schedule of Procedures and Visits (Table 1) for the detailed plan.

Figure 1. Schematic of APD334-010 Study Design

^a Screening Visit 1 is to occur between Week -8 and Week -5. Screening Visit 2 is to occur at least 4 weeks from Screening Visit 1. For patients with ALP, ALT, AST, or total bilirubin values from Screening Visits 1 and 2 that are not within 20% of each other (see Inclusion Criterion 9), an unscheduled visit within the screening period may be conducted to repeat these assessments.

The study will consist of the following periods:

Screening Period (5 to 8 weeks before baseline visit):

Each patient will be asked to visit the study site at least 2 times for screening assessments within the 8 weeks prior to the planned start of the treatment (Day 1). Screening Visit 1 is to occur between Week -8 and Week -5. Screening Visit 2 is to occur at least 4 weeks from Screening Visit 1. For patients with ALP, ALT, AST, or total bilirubin values from Screening Visits 1 and 2 that are not within 20% of each other (see Inclusion Criterion 9), an unscheduled visit within the screening period may be conducted to repeat these assessments.

All patients must be consented before any study specific procedure is performed and written informed consent must be obtained. Patients will then undergo screening procedures to determine eligibility.

Treatment Period (24 weeks):

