3.2. Study Duration

[figure not shown]
The study duration will be up to 34 weeks per patient, with 5 to 8 weeks for screening, followed by a 24-week treatment period (including a 12-week 1 mg treatment period followed by a 12-week 2 mg treatment period if tolerable) and a follow-up visit 2 weeks after the end of treatment.

[figure not shown]
The Schedule of Procedures and Visits for the study is provided in Table 1.

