6.15. Adverse Events Assessments

Patients will be monitored from ICF signature to 30 days after the last dose of study drug for AEs to the study drug and/or procedures.

AEs will be recorded and reported in accordance with ICH GCP. The definitions of AEs and serious AEs (SAEs) will be as given in ICH Guideline E2A, “*Clinical Safety Data Management: Definitions and Standards for Expedited Reporting*.” The outcome of an AE will be defined according to ICH Guideline E2B(R3), “*Clinical Safety Data Management: Data Elements for Transmission of Individual Case Safety Reports*.” The relationship to investigational product will be classified using World Health Organization (WHO) criteria.

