6.15.1. Adverse Event Reporting

Patients will be instructed to report all AEs, which can be reported at any time. AEs that occur from ICF signature until the time of administration of the first dose of etrasimod will be regarded as ‘pre-treatment’ and recorded as an AE. All events reported following study medication administration up to 30 days after the last medication intake will be presented as treatment emergent AEs (TEAEs).

Monitoring of ongoing AEs will be continued up to 30 days after study medication administration.

[figure not shown]
For this study, an AE is defined as: “Any untoward medical occurrence in a study patient administered etrasimod which does not necessarily have to have a causal relationship with this treatment.” An AE can therefore be any unfavorable and unintended sign (including an abnormal

laboratory finding), symptom, or disease temporally associated with the use of the study medication, whether or not related to the product. AEs can be any of the following:

- Unfavorable changes in general condition
- Subjective or objective signs/symptoms
- Concomitant disease or accidents
- Clinically relevant adverse changes in laboratory parameters observed in a patient in the course of a clinical study
- Pre-existing conditions which worsen in severity or frequency or which have new signs/symptoms associated with them

Lymphopenia will not be captured as an AE because it is an expected pharmacologic effect of the drug.

AEs will be elicited at the time indicated in the schedule. Any adverse or unexpected events, signs and symptoms will be fully recorded on the AE Form including details of intensity, onset, duration, outcome and relationship to the drug as determined by the PI. Whenever possible, a constellation of signs and symptoms should be recorded as a unifying diagnosis (e.g., self-limited fever, runny nose, cough, and scratchy throat should be captured as an upper respiratory infection rather than by the individual signs and symptoms). AEs may also be reported at any time. The type and duration of follow-up of patients after AEs will be documented.

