9.7. Safety Analysis

Safety and tolerability will be assessed by a review of all safety parameters including AEs, laboratory safety parameters, [REDACTED] vital signs, and ECG. AEs will only be presented as summary tabulations. When assessing change from baseline, a baseline measurement is also required. Baseline for the safety analysis is defined as the average of the pre- dose measurements. No missing data will be imputed for the safety analysis. For continuous variables, summary statistics (N, mean [or median], SD, mean [or median] change/percent change) and 95% CI will be produced if applicable; for proportion-based measures, N, frequencies, proportion and its 95% CI will be produced.

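### AE tables split by treatment and follow-up period have no patient-time denominator, so periods of 24 weeks and about 2 to 4 weeks invite a misleading comparison

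*Combined protocol and SAP*

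**What the plan says.** The Statistical Analyses row of the synopsis plans to evaluate safety by "tabulating adverse events and clinical assessment of clinical laboratory data by treatment period and follow up period". Section 9.7 states that "AEs will only be presented as summary tabulations" and that "for proportion-based measures, N, frequencies, proportion and its 95% CI will be produced". No visible section mentions patient-weeks, an exposure-adjusted rate, or a caution about comparing periods of unequal length.

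The period lengths come from elsewhere. Section 3.2 describes a "24-week treatment period (including a 12-week 1 mg treatment period followed by a 12-week 2 mg treatment period if tolerable", so it uses the same term for the whole 24 weeks and for each 12-week dose block. Section 3.1 places the last dose one day before the end of treatment and adds: "A follow-up visit will take place 2 weeks after the end of treatment". Section 6.15 sets a longer AE window: "Patients will be monitored from ICF signature to 30 days after the last dose of study drug for AEs".

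Section 9.7.1 does not repeat the synopsis split. It has only two classes, pre-treatment and treatment-emergent, and gives the second no end date. Section 6.15.1 ends the treatment-emergent class 30 days after the last intake. Under either definition, follow-up events are pooled with on-treatment events. Section 9.7.1 also tabulates onset relative to dose and plans listings by patient.

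**The concern.** The proportion of patients with at least one AE rises with the time they are watched. Two proportions from windows that differ this much in length are not comparable, even when the underlying rate is the same. A background complaint that recurs at a steady rate would show a high percentage in the treatment column and a low one in the follow-up column. A reader could take that as an effect of the drug that reverses on stopping.

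Safety and tolerability is the only primary objective (Section 2.1) and there is no control group (Section 9.1), so readers will look for contrasts within the trial. Background events are plausible in this population. Section 1.1 describes fatigue and pruritus as frequent symptoms of PBC, and Section 6.15.1 counts worsening of a pre-existing condition as an AE.

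**Working it through.** The plan states no AE rate, power or calculated sample size, so there is no figure of its own to reproduce. The check asks what the planned statistic would show if the drug had no effect on AEs.

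**Inputs from the documents**
- Treatment: 24 weeks = 168 days (Section 3.2).
- Follow-up to the last visit: last dose one day before the Week 24 visit, then 2 weeks, so 1 + 14 = 15 days = 2.14 weeks (Section 3.1).
- Follow-up by AE capture: 30 days = 4.29 weeks (Sections 6.15 and 6.15.1).
- Up to 20 patients.

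**Assumption.** A constant first-event rate λ, the same in both periods, of 0.02, 0.05 or 0.10 per patient-week.

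**Time at risk.** 168/15 = 11.2 and 168/30 = 5.6.

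**Proportion with at least one AE in t weeks** = 1 − exp(−λt):

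| λ per week | 24 weeks | 15 days | Ratio | 30 days | Ratio |
|---|---|---|---|---|---|
| 0.02 | 38% | 4% | 9.1 | 8% | 4.6 |
| 0.05 | 70% | 10% | 6.9 | 19% | 3.6 |
| 0.10 | 91% | 19% | 4.7 | 35% | 2.6 |

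For example, at λ = 0.05: 1 − exp(−1.2) = 0.699, 1 − exp(−0.107) = 0.102, and 0.699/0.102 = 6.9. The ratio therefore runs from 2.6 to about 9 with no drug effect. For rare AE terms it approaches the time ratio itself.

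**More than sampling noise.** Take 50% incidence over 24 weeks (λ = 0.029), n = 20, and the two columns simulated as independent binomials. The follow-up proportion falls below half the treatment proportion in 99% of trials with a 2-week follow-up and in 90% with a 30-day follow-up.

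**What shrinks it**
- Heterogeneity between patients: with gamma frailty of variance v, the proportion is 1 − (1 + λtv)^(−1/v). The ratios below are for 2-week / 30-day follow-up.
  - v = 1: 6.5 / 3.3 at 50% incidence over 24 weeks, and 3.2 / 1.9 at 80%.
  - v = 2: 4.7 / 2.6 at 50%, and 1.9 / 1.4 at 80%.
- Less treatment time: with 12 weeks on treatment instead of 24, the time ratio falls to 12/2 = 6.0 or 12/4.29 = 2.8. At 50% incidence over those 12 weeks the proportion ratio is 4.6 or 2.3.

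**With a patient-time denominator.** For first events the expected time at risk per patient is (1 − exp(−λt))/λ. At λ = 0.05 and 20 patients, treatment gives 20 × 0.699 = 14.0 first events in 20 × 0.699/0.05 = 280 patient-weeks at risk. The 15-day follow-up gives 20 × 0.102 = 2.0 in 20 × 0.102/0.05 = 41. Both rates equal 0.05 per week, so the artefact is gone.

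**The case against.** The best defence is that no on-drug versus off-drug comparison is planned. The synopsis only sorts events by when they occurred, Section 9.1 specifies no hypothesis tests, and Section 9.6.1 plans no inferential comparisons for study endpoints. The period lengths are stated openly. The split appears only in the synopsis, while Sections 6.15.1 and 9.7.1 pool follow-up events with on-treatment ones. Onset relative to dose, with listings by patient, shows in at most 20 patients much of what a reader needs. That simple proportions will be used is itself inferred, by joining the synopsis to a general sentence in Section 9.7.

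Most of this stands, and it makes this a reporting point, not an analysis error. It does not remove the point. The synopsis does name the split, the only statistic offered is sensitive to period length, and onset timing supplies no denominator. The mismatch between the synopsis and Section 9.7.1 also leaves unclear which table will be produced.

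A second objection is that rates would be too imprecise to help. Two events in 43 patient-weeks give an exact Poisson 95% CI of about 0.006 to 0.17 per week, a 30-fold range. Nor is follow-up cleanly off drug, since Section 6.12.1 provides for lymphocyte counts that have not recovered at Week 26. Both remarks are fair. A wide interval is still the honest picture of what a short follow-up can show.

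Three stronger readings are tempting but unsupported.
- A reader might infer that 1 mg will look worse than 2 mg because it carries more patient time. No visible passage commits to AE tables by dose. Escalation also depends on time and on each patient's own safety and PK data (Sections 1.3.2 and 5.5), so patient-weeks alone could not make the doses comparable.
- A reader might think that early stoppers aggravate the imbalance. They shorten the treatment period and so narrow it.
- A reader might treat a several-fold fall as certain. Its size depends on rates that the documents do not give.

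**Conclusion.** The point holds as a reporting weakness in the primary safety summary of an uncontrolled trial. As planned, the tables by period would show a proportion with an AE about 2.6 to 9 times lower in follow-up even if the rate never changed. This rests on a constant rate of 0.02 to 0.10 first events per patient-week, full 24-week treatment, and follow-up of 15 or 30 days. With strong heterogeneity between patients the ratio can fall below 2. The harm arises only if a descriptive table is read as a rate comparison. The documents do not show a biased test or a flawed dose comparison. Separately, the two periods are not defined by date, and the synopsis does not match the treatment-emergent classes in Sections 6.15.1 and 9.7.1.

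**What to change.** In the synopsis and in Sections 9.7 and 9.7.1:

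- Define the treatment and follow-up periods by date. State whether follow-up ends at the Week 26 visit or at 30 days, and whether treatment period means the 24 weeks or a 12-week dose block.
- Reconcile these periods with the treatment-emergent definitions in Sections 6.15.1 and 9.7.1.
- Print patient-weeks at risk in each column.
- Beside n (%), add patients with a first event in the period per patient-week at risk, with an exact Poisson 95% CI. Time at risk ends at that first event.
- Add event counts per patient-week, either as description only or with an interval that allows for repeat events within a patient.
- If AEs are also shown by dose at onset, do the same there, and note that dose is confounded with time on study and with selection for escalation.

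The cost is wording and a little programming, because onset and dosing records are already collected (Sections 5.2 and 6.15.1). There are two drawbacks. Follow-up intervals will be wide, since 20 patients contribute at most 20 × 15/7 = 43 or 20 × 30/7 = 86 patient-weeks. The rates also assume a roughly constant hazard within each period.
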